Transfer from Part A to Part B: Since Part A will be the first time patients in intensive care are receiving ETX2514SUL, PK in the first approximately 30 patients must be verified prior to initiating Part B to ensure the treatment planned in Part B is optimal for the targeted patient population. Patients randomized to either group of Part A can only be transferred to Part B, once Part B is open for enrollment, if the ABC identified from the baseline culture is subsequently determined to be resistant to colistin or polymyxin B by the local microbiology laboratory. If Part B is not yet open for enrollment in a given country and a patient in Part A has a baseline culture determined to be colistin- or polymyxin B-resistant but is responding to therapy, the patient may remain in Part A at the discretion of the Investigator. A patient in Part A whose culture is determined to be colistin- or polymyxin B-resistant and who has not shown improvement or whose condition has worsened will be withdrawn from the study drug treatment. All such cases must be discussed with the Medical Monitor.

Any organism isolated from the blood or infection site-specific cultures will be identified by genus and species by the local laboratory. Organisms will be cultured and quantified (urine and bronchoalveolar lavage [BAL] only) at the local laboratory, and susceptibility of the organism(s) will be performed per local laboratory standards. Isolates of pathogens cultured at the local laboratory are to be sent to the central laboratory for confirmation of identification and susceptibility testing.

[figure not shown]

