### 5.4 Randomization and Blinding

Qualifying patients enrolling in Part A will be randomized in a 1:1 ratio to receive 1.0 g ETX2514/1.0 g sulbactam q6h plus 1.0 g imipenem/1.0 g cilastatin q6h or 2.5 mg/kg colistin q12h plus 1.0 g imipenem/1.0 g cilastatin q6h via the Interactive Response Technology (IRT) system. Patients enrolled in the study based on the positive BPP rapid test results but are found to not grow

ABC in respiratory specimen cultures by the local microbiology laboratory will be withdrawn from the study drug treatment as detailed in [Section 4.3](#).

Randomization in Part A will be stratified by indication (HABP/VABP/VP versus bacteremia), severity of illness (based on APACHE II [10 to 19 versus 20 to 30], SOFA [7 to 9 versus  $\geq 10$ ], or qSOFA [2 versus 3] score at Screening), and geography (China Mainland versus Rest of World). In the situation where a patient has more than one score reported, the scores will be used in the following order: APACHE, SOFA, and qSOFA. A quick reference guide will be provided that describes the IRT system and includes user instructions. Enrollment of HABP, VP, and bacteremia patients will be limited to a total of no more than 40% of patients in Part A, regardless of resistance.

The study data will be collected and handled as if it were a blinded study. The blinded assessor (see Section 5.4.2), the Sponsor, and the Sponsor's designees involved in medical and safety monitoring, data management, and other aspects of the study (eg, interpretation of the results) will be blinded to treatment assignment. Given the complexity of the regimens, the Principal Investigator, other care givers, the clinical research associate (CRA), and other site personnel (eg, study coordinators and pharmacy staff) will be unblinded (see Section 5.4.1). Patients will not be informed of their treatment assignment, and efforts will be made to keep patients naïve to their treatment throughout the course of the study.

Part B is open-label and not randomized; all patients enrolling in Part B will receive 1.0 g ETX2514/1.0 g sulbactam q6h plus 1.0 g imipenem/1.0 g cilastatin q6h.

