The local laboratory will culture each sample for species identification, quantification (urine and BAL only), and susceptibility testing. Any organism isolated from the culture will be identified by genus and species by the local laboratory. Potential pathogen(s) cultured at the local laboratory, including species isolated from mixed infections with other Gram positive or Gram negative organisms, will be sent to a designated central laboratory for confirmation of species identification, susceptibility testing results, and potential molecular characterization.

All organisms identified on culture at the local laboratory and the local laboratory assessment of susceptibility testing for each organism will be captured in the eCRF.

Enrollment in Part A can occur after ABC is identified in the blood and/or other respiratory tract specimens but prior to establishing the resistance profile. If local laboratory susceptibility testing reveals colistin resistance after a patient has been randomized to Part A, the patient must be transferred to Part B, regardless of the treatment group assignment in Part A, once Part B is open for enrollment. If Part B is not open for enrollment, patients will be withdrawn from the study drug treatment.

Patients who are randomized to Part A based on a positive screening of a respiratory sample for ABC by BPP rapid test, but subsequently do not have growth of ABC in their respiratory sample culture processed by the local microbiology laboratory, will be withdrawn from the study drug treatment. The need for continued standard of care treatment should be assessed by the Investigator.

When a patient's culture grows Gram positive organisms but the patient is clinically improving, the patient may remain on study drug without additional Gram positive antibiotic coverage at the Investigator's discretion. Patients who are not clinically improving or need adjustment in antimicrobial therapy that is not allowed per the protocol should be discontinued from study drug at the discretion of the Investigator, but should remain in the study to complete all study assessments. Additional cultures and all EOT procedures should be performed at the time of discontinuation and every attempt must be made to collect survival data at Day 28 or anytime thereafter.

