### 2.2. Secondary Objectives

The secondary objectives of this study are the following:

- To compare the efficacy of ETX2514SUL plus imipenem/cilastatin to colistin plus imipenem/cilastatin in all randomized patients in Part A;
- To evaluate the efficacy of ETX2514SUL plus imipenem/cilastatin in patients with colistin- or polymyxin B-resistant ABC infections in Part B;
- To estimate the efficacy of ETX2514SUL plus imipenem/cilastatin for each primary infection site;
- To evaluate and compare the safety of ETX2514SUL and colistin;
- To describe the overall safety profile of ETX2514SUL; and
- To determine the systemic exposure of ETX2514 and sulbactam in a small cohort of severely ill patients administered ETX2514SUL in Part A.

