#### **9.1.3. Baseline Definition**

For microbiological data, baseline pathogen(s) are determined from the specimens collected prior to the first dose of study drug.

For all efficacy and safety endpoints, baseline is defined as the last measurement or assessment prior to the first dose of study drug.

For safety endpoints, patients who were randomized into Part A then transferred into Part B will be included in both Part A and Part B, baseline is defined as the last measurement or assessment prior to the first dose of study drug of Part A for both Part A and Part B safety analysis.

For efficacy endpoints, patients who were randomized into Part A then transferred into Part B will be included in Part B only, baseline is defined as the last measurement or assessment prior to the first dose of study drug of Part A for Part B efficacy analysis.

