#### **9.4. Safety Analyses**

All safety summaries and analyses will be performed on the Safety Population. All patients will be summarized based on the actual treatment received. Safety endpoints include the assessment of adverse events and the evaluation of changes from baseline in safety laboratory test results, ECGs, vital signs, and physical examinations.

For each safety endpoint, unless otherwise stated, the last assessment made prior to the first administration of study drug will be used as the baseline value for all analyses.

The safety analyses will be analyzed for Part A and Part B separately. For the patients who were randomized into Part A but then transferred into Part B, safety will be summarized/analyzed until the date of transfer for Part A; safety reported on or after the date of transfer will be summarized/analyzed for Part B. Baseline is the last measurement or assessment prior to the first dose of study drug of Part A for both Part A and Part B safety analysis.

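### For patients moved from colistin to ETX2514SUL, the Part B safety baseline predates study colistin, so Part B changes from baseline include change that arose on colistin

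*SAP*

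**What the plan says.** **Baseline.** SAP 9.4 states the rule for transferred patients: the reference value is the last one obtained "prior to the first dose of study drug of Part A for both Part A and Part B safety analysis". SAP 9.1.3 gives the same rule and adds that, for safety endpoints, "patients who were randomized into Part A then transferred into Part B will be included in both Part A and Part B". The choice is explicit and appears twice.

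**Where the data go.** SAP 9.4 summarizes patients by the treatment they actually received and divides the safety data of transferred patients at the transfer date: "safety reported on or after the date of transfer will be summarized/analyzed for Part B".

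**Who transfers, and to what.** Protocol 3.1 opens transfer to both arms: "Patients randomized to either group of Part A can only be transferred to Part B, once Part B is open for enrollment", on a local finding of colistin or polymyxin B resistance. Protocol 7.7 says that on such a result "the patient must be transferred to Part B, regardless of the treatment group assignment in Part A". Under Protocol 5.4, "all patients enrolling in Part B will receive 1.0 g ETX2514/1.0 g sulbactam q6h plus 1.0 g imipenem/1.0 g cilastatin q6h".

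**What is reported for Part B.** SAP 9.4.2 plans laboratory change from baseline for both parts, with shift tables whose chemistry list includes creatinine, ALT, AST, total bilirubin and potassium. Its liver-threshold percentages use patients who were normal at baseline as the denominator. SAP 9.4.3 and 9.4.4 plan vital-sign and ECG changes from baseline, the latter with counts of maximum QTcF change above 30 and 60 msec.

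No section gives a transfer-time baseline for patients coming from colistin, a separate summary of them, or an analysis without them.

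**The concern.** Part B is a single-group cohort treated with ETX2514SUL, so a reader will take a Part B change from baseline as change seen on that drug. For a patient who spent the first days of the study on colistin, part of that change happened before any ETX2514SUL was given. The SAP divides the data by treatment at the transfer date but does not move the reference value with it.

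Describing the overall safety profile of ETX2514SUL is a secondary objective (SAP 2.2), and Protocol 1.3 says that its safety is to be assessed across both parts together. Protocol 1.4 acknowledges that colistin carries a risk of nephrotoxicity, so creatinine is the measure where carry-over is most likely.

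**Working it through.** The documents give no figure to reproduce here. The check compares the rules and then illustrates their arithmetic effect.

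**Step 1: what baseline means for each route into Part B.**

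| Route into Part B | Safety baseline under the SAP | Position relative to first ETX2514SUL dose |
|---|---|---|
| Enrolled directly | Last value before first study drug | Immediately before |
| Transferred from the ETX2514SUL arm | Last value before first Part A dose | Immediately before |
| Transferred from the colistin arm | Last value before first Part A dose | Before study colistin, so separated by the whole colistin period |

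Only the third row is out of line. Patients enrolled directly after failing non-study colistin or polymyxin B (Protocol 4.1.3) have that earlier exposure absorbed into their baseline. For colistin-arm transfers, study colistin is counted as change instead.

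**Step 2: one patient.** Let Y0 be the value before the first Part A dose, YT the last value before the first Part B dose, and Yt a later Part B value.

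- SAP rule: Part B change = Yt − Y0 = (YT − Y0) + (Yt − YT).
- Transfer baseline: Part B change = Yt − YT.

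The difference, YT − Y0, arose entirely on study colistin. With assumed creatinine of 1.0 mg/dL before colistin, a rise by transfer, and no change on ETX2514SUL:

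| Creatinine at transfer (mg/dL) | Change shown in Part B, SAP rule | Change from transfer baseline |
|---|---|---|
| 1.5 | 1.5 − 1.0 = +0.5 | 0 |
| 2.0 | 2.0 − 1.0 = +1.0 | 0 |
| 3.0 | 3.0 − 1.0 = +2.0 | 0 |

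In the shift table, if the laboratory's upper limit lies between 1.0 and 2.0 mg/dL, the second patient moves from normal to the first raised category under the SAP rule. With a transfer baseline the same patient starts and stays in the raised category.

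**Step 3: the Part B mean.** Let f be the share of patients in a given Part B table and visit who came from colistin, and d their mean change before transfer. The mean Part B change is shifted by f × d. Neither f nor d can be taken from the documents, so a range of assumed values is shown (creatinine, mg/dL):

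| f | d = 0.5 | d = 1.0 | d = 2.0 |
|---|---|---|---|
| 5% | 0.025 | 0.05 | 0.10 |
| 10% | 0.05 | 0.10 | 0.20 |
| 25% | 0.125 | 0.25 | 0.50 |
| 50% | 0.25 | 0.50 | 1.00 |

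SAP 9.4.2 splits the laboratory tables between Mainland Chinese and other patients, so f may differ between the two sets.

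**Step 4: outputs that do not depend on this baseline.**

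- The RIFLE summary and the chi-square test (SAP 9.4.1) are planned for Part A only.
- Adverse events are assigned by transfer date.
- ALT, AST and bilirubin elevations are fixed multiples of the upper limit of normal; baseline sets only the denominator.
- The QTcF counts above 450, 480 and 500 msec are absolute.

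**The case against.** **The convention is defensible.** It is stated consistently, matches the SAP's general rule of the last value before first study drug, and measures change from the state before study treatment. The tables are descriptive and assign no cause. This is a fair account of why the rule was written. It does not explain why a cohort defined by ETX2514SUL should have a reference value separated from that drug by a course of colistin.

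**The rule is conservative.** It counts against ETX2514SUL when colistin has done harm, but it can also work the other way. Protocol 4.2, exclusion criterion 16, allows entry with infection-related AST or ALT up to 5 times the upper limit. If ALT falls to normal on colistin and then rises on ETX2514SUL, Part B may show no increase from the pre-colistin value. The patient, abnormal at baseline, also drops out of the liver-threshold denominator.

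**A transfer baseline has its own bias.** It is an on-treatment value. Recovery from colistin injury would look like improvement on ETX2514SUL, delayed colistin effects would still appear in Part B, and a patient abnormal at transfer would leave the normal-at-baseline denominator. All of this stands, and it is the reason to show both baselines for these patients.

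**Little depends on it.** Part B is open-label and supportive, known colistin-resistant infections are excluded from Part A (criterion 27), transfers may be few, and all laboratory data are listed. These points stand and limit the importance.

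**A stronger reading to avoid.** A reader might infer that colistin nephrotoxicity will be counted as RIFLE events against ETX2514SUL, or that each transfer moves a Part B nephrotoxicity percentage by a definite amount. The documents plan no Part B RIFLE percentage and state neither the size of Part B nor the number of transfers, so they do not support that.

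**Conclusion.** The point holds for baseline-referenced Part B safety outputs in colistin-arm transfers: laboratory changes and shift tables, vital-sign and ECG changes including the QTcF change categories, and the denominator of the liver-threshold percentages. In these outputs, change that occurred on study colistin is reported as change in the ETX2514SUL cohort, against the SAP's own division of safety data by treatment received.

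Its size cannot be fixed from the documents. The shift in a mean is f × d, and the creatinine figures above rest on assumed values of both. Here, before colistin means before study colistin; Protocol 5.2 recognizes that some patients may already be on colistin at randomization.

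The primary efficacy analysis and the Part A nephrotoxicity comparison are untouched. This is a minor point, worth correcting because correction is cheap.

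**What to change.** In SAP 9.1.3 and 9.4:

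- For patients randomized to colistin who transfer, define the Part B safety baseline as the last value before the first Part B dose of ETX2514SUL.
- Keep the pre-Part A baseline for all Part A summaries and for transfers from the ETX2514SUL arm.
- Report the number of colistin-arm transfers, and show them separately with changes from both the transfer baseline and the pre-Part A baseline.

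The cost is a sentence in each section and one small table. Most of the data should exist: creatinine is measured daily on study drug, and chemistry is scheduled on Days 1, 3, 5 and 7. ECGs are sparser. The last tracing before transfer may be the one after the first infusion on Day 1, so the change does less for QTcF.

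The downside is that Part B then carries two baseline rules by calendar reference, although both amount to the last value before ETX2514SUL. Delayed colistin effects, or recovery from them, after transfer remain in the Part B data, and a footnote should say so.

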#### 9.4.1. Adverse Events

A treatment-emergent adverse event (TEAE) is defined as an adverse event occurring on or after the administration of the first dose of study drug. An overview of adverse events will be provided which summarizes the incidence of the following categories:

- All AEs,
- All TEAEs,
- Drug-related TEAEs,
- TEAEs by severity,
- SAEs,
- Drug-related SAEs,
- SAE leading to death,
- TEAE leading to discontinuation of study drug, and
- SAE leading to discontinuation of study drug.

Patients with multiple events will be counted only once within each category. Severity grade and relationship will be counted using the maximum severity and the strongest relationship respectively for a patient with multiple TEAEs.

The number and percentage of patients reporting a TEAE in each treatment group will be tabulated by SOC and PT; by SOC, PT, and severity; and by SOC, PT, and relationship (related or unrelated to study drug and imipenem/cilastatin). Summary tables will be presented alphabetically by SOC and decreasing frequency of PT in the EXT2514SUL group within SOC. For all analyses of TEAEs, if the same AE (based on PT) is reported for the same patient more than once, the AE is counted only once for that PT and at the highest severity and strongest relationship to study drug.

The number and percentage of patients reporting a drug-related TEAE, a SAE, a treatment emergent SAE, a drug-related treatment-emergent serious adverse event (TESAE), and a TEAE leading to discontinuation of study drug in each treatment group will be summarized by SOC and PT.

A list of patients who have SAEs, a list of patients who discontinue from study drug, and a list of death will be provided. All adverse events will be listed.

#### Adverse Events of Special Interest

Adverse events of special interest and their definitions include the following:

- Allergic and hypersensitivity reactions: Severe and serious adverse drug reactions from the Medical Dictionary for Regulatory Activities (MedDRA) Standardized MedDRA Queries of allergy and hypersensitivity,
- Nephrotoxicity: Using the RIFLE criteria for the duration of the study (see Table 2)1, and

- Emergent infections and superinfections: All serious and severe events in the MedDRA system organ class of infections and infestations other than the indication infection (ie, ABC).
- Clostridioides difficile infection

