- ETX2514 was predominantly excreted renally and dose adjustments were necessary for patients with moderate or severe renal insufficiency including dialysis. Similarly, higher doses are recommended for patients with augmented renal clearance or receiving continuous renal replacement therapy.
- ETX2514SUL demonstrated good penetration of the lung epithelium.

Efficacy results:

- ETX2514SUL when dosed with imipenem/cilastatin showed comparable efficacy to placebo + imipenem/cilastatin in treatment of hospitalized patients with cUTI or AP. Among patients with imipenem nonsusceptible infections, imipenem combined with ETX2514SUL was able to successfully treat 3 out of 3 infections.

Safety and tolerability results:

- ETX2514 was generally safe and well tolerated when given alone or with sulbactam and/or imipenem/cilastatin.
- To date, there have been no serious adverse drug reactions or deaths in clinical studies.
- The most common adverse events reported were headache and infusion site reactions, including phlebitis and vascular pain at the infusion site.
- Mild reductions in total white blood cell (WBC) and absolute neutrophil counts have been observed with multiple doses of ETX2514, although no events of leukopenia or neutropenia have been observed.
- Asymptomatic, transient increases in hepatic enzymes (unaccompanied by increases in bilirubin) have been observed with ETX2514SUL, and these are thought to be related to known effects of sulbactam.
- Mild to moderate allergic reactions including urticaria have been observed at rates <1% with ETX2514SUL.
- No clinically significant changes in vital signs or electrocardiogram (ECG) parameters have been observed in patients treated with ETX2514SUL. Transient increases in systolic blood pressure within normal ranges were observed in healthy elderly subjects dosed with ETX2514SUL.
- ETX2514, at the studied doses, had no clinically relevant effects on studied ECG parameters in a thorough QT study conducted in healthy volunteers.

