#### 8.1.4 Adverse Events of Special Interest

Adverse events of special interest will be analyzed, summarized, and reported in the clinical study report. Statistical comparisons will be made between the investigational and control groups in Part A.

Adverse events of special interest and their definitions include the following:

- Allergic and hypersensitivity reactions: Severe and serious adverse drug reactions from the Medical Dictionary for Regulatory Activities (MedDRA) Standardized MedDRA Queries of allergy and hypersensitivity;
- Nephrotoxicity: Using the RIFLE criteria for the duration of the study (see Table 6), and
- Emergent infections and superinfections: All serious and severe events in the MedDRA system organ class of infections and infestations other than the indication infection (ie, ABC).

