#### 9.2.4 Analysis of Safety

All patients who receive any amount of study drug (MITT Population) will be included in the safety analyses. Patients who received the wrong study drug for their entire course of treatment will be analyzed in the group based on the drug received.

A primary analysis of safety will be performed for Part A to assess the proportion of patients with nephrotoxicity, as measured by the RIFLE criteria based on the Safety and CE Populations.

Overall safety will be assessed for Part A and Part B in the Safety Population. The number and percentage of patients in each treatment group reporting at least 1 occurrence of a TEAE for each unique system organ class and preferred term will be tabulated. A TEAE is defined as an adverse event occurring on or after the administration of the first dose of study drug. Treatment-emergent adverse events will also be tabulated by treatment group, severity, and the relationship to study drug as assessed by the Investigator. The number and percentage of patients in each treatment group reporting at least 1 occurrence of a treatment-emergent SAE will be tabulated. The number and percentage of patients (in each treatment group) prematurely discontinuing study drug treatment due to a TEAE will be tabulated by system organ class and preferred term. Adverse events of special interest in Part A will be summarized for all patients by treatment.

Safety laboratory data will be presented by descriptive statistics of the post-baseline value and the change from baseline, as well as the number and percentage of patients with potentially clinically significant laboratory values. Descriptive statistics of vital signs and ECG parameters and the change from baseline will also be presented. An outlier analysis of the ECG parameters will be conducted.

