**Table 2. Definition of RIFLE Criteria**

Term	Definition
Risk (R)	Increased creatinine level 1.5× or GFR decrease >25%
Injury (I)	Increased creatinine level 2× or GFR decrease >50%
Failure (F)	Increased creatinine level 3×, GFR decrease >75%, or creatinine level ≥4 mg/dL
Loss (L)	Persistent acute renal failure or complete loss of function for >4 weeks
ESKD (E)	ESKD for >3 months

ESKD = end-stage kidney disease; GFR = glomerular filtration rate; RIFLE = Risk–Injury–Failure–Loss–End-stage renal disease.

The number and percentage of patients reporting adverse events of special interest will be summarized by each category and treatment group in Part A in the Safety and CE Populations. In addition, proportion of patients with nephrotoxicity will be compared between the investigational and control groups using Chi-square test. The Chronic hemodialysis patients will not be included in the nephrotoxicity analysis.

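### Protocol 8.1.4 plans between-arm comparisons of adverse events of special interest in Part A, but SAP 9.4.1 carries this out only for nephrotoxicity

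*SAP*

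**What the plan says.** Protocol 8.1.4 introduces the adverse events of special interest with a general statement: "Statistical comparisons will be made between the investigational and control groups in Part A". It then lists three categories: allergic and hypersensitivity reactions, nephrotoxicity by RIFLE, and emergent infections and superinfections.

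Protocol 9.2.4, in the statistics chapter, is more modest: "Adverse events of special interest in Part A will be summarized for all patients by treatment".

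SAP 9.4.1 repeats the three categories and adds Clostridioides difficile infection. It plans the number and percentage of patients per category and arm in Part A, in the Safety and CE Populations. One comparison follows: "In addition, proportion of patients with nephrotoxicity will be compared between the investigational and control groups using Chi-square test". The SAP contains no other test or interval for a special-interest category. One secondary objective, in SAP 2.2, reads "To evaluate and compare the safety of ETX2514SUL and colistin".

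The hypersensitivity category is defined identically in both documents: "Allergic and hypersensitivity reactions: Severe and serious adverse drug reactions from the Medical Dictionary for Regulatory Activities", selected through the standardized queries for allergy and hypersensitivity. On earlier experience, Protocol 1.2 reports: "Mild to moderate allergic reactions including urticaria have been observed at rates <1% with ETX2514SUL".

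**The concern.** The sentence in Protocol 8.1.4 comes before the list and is not limited to one item. Read plainly, it covers hypersensitivity and emergent infections as well as nephrotoxicity. The SAP, where the protocol says the safety analysis will be set out in detail, drops two of the three comparisons without comment. The study report would then either lack an analysis that the protocol announced or supply one whose method was chosen after the data were seen.

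The second matter concerns what the hypersensitivity row can show. Protocol 1.4 names allergic and hypersensitivity reactions as a potential risk. The only grouped count planned for that risk is filtered to severe and serious drug reactions. If reactions in this trial resemble those seen so far and are non-serious, that row reads zero in both arms however many patients had one.

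**Working it through.** **Step 1: the texts side by side.**

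| Category | Protocol 8.1.4 | Protocol 9.2.4 | SAP 9.4.1 |
|---|---|---|---|
| Nephrotoxicity | compare | summarize (also the primary safety analysis) | counts and chi-square test |
| Hypersensitivity | compare | summarize | counts only |
| Emergent infections | compare | summarize | counts only |
| C. difficile infection | not listed | not listed | counts only |

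The SAP agrees with 9.2.4 but not with 8.1.4. Both protocol sentences can be satisfied together, since a comparison can sit beside a summary. The later one therefore does not cancel the earlier one.

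**Step 2: what the other safety tables give.** SAP 9.4.1 tabulates treatment-emergent events of every grade by system organ class and preferred term, also by severity and by relationship. For a repeated event, "the AE is counted only once for that PT and at the highest severity and strongest relationship to study drug". These rows count patients per term. A patient with two hypersensitivity terms appears in two rows, so the rows cannot be summed to patients with any hypersensitivity event. No planned row applies the queries at all grades.

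**Step 3: numbers per arm.** The plan gives no figure for these analyses. Its enrolment figure reproduces: 120 / 0.60 = 200 in Part A, so about 100 per arm at 1:1.

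**Step 4: hypersensitivity.** Protocol 1.2 gives only a rate below 1%. Assume r = 0.25%, 0.5% or 1% on the test drug. The expected number of patients is 100r and the chance of at least one is 1 - (1 - r)^100.

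| r | Expected | Chance of at least one |
|---|---|---|
| 0.25% | 0.25 | 22.1% |
| 0.5% | 0.5 | 39.4% |
| 1% | 1.0 | 63.4% |

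The Newcombe 95% interval for p1 - p2 combines the Wilson limits (l, u) of each arm:

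lower = d - sqrt[(p1 - l1)^2 + (u2 - p2)^2]; upper = d + sqrt[(u1 - p1)^2 + (p2 - l2)^2].

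- 0/100: Wilson limits 0 and z^2/(n + z^2) = 3.84/103.84 = 0.0370.
- 1/100: Wilson limits 0.0018 and 0.0545.
- 0/100 vs 0/100: -3.7 to +3.7 points.
- 1/100 vs 0/100: lower = 0.01 - sqrt(0.0082^2 + 0.0370^2) = -0.0279; upper = 0.01 + 0.0445 = 0.0545. That is -2.8 to +5.5 points.

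The continuity-corrected Z interval that the SAP uses for efficacy should not be borrowed here. At 0 vs 0 its standard error is zero and only the correction 0.5 × (1/100 + 1/100) = 0.01 remains, giving -1.0 to +1.0 points, which is far too narrow.

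These figures describe reactions at the rate reported so far. They do not estimate an all-causality query count in severely ill patients, for which the documents give no rate.

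**Step 5: emergent infections.** The documents give no rate. Assuming equal rates in both arms, the Newcombe half-width is 8.7 points at 10%, 11.1 at 20% and 12.6 at 30%.

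**Step 6: tests or intervals.** Four independent tests at 5% would give a chance of 1 - 0.95^4 = 18.5% of at least one false positive. This favours intervals labelled descriptive over further tests.

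**The case against.** The best defence is that Protocol 8.1.4 names no method and does not say that each category will be tested. The statistics chapter asks only for a summary, and the SAP delivers it. The one category tested belongs to a primary objective, and comparing safety can mean setting percentages side by side. Much of this stands: the SAP is faithful to 9.2.4, and the gap is one of alignment. It does not explain why a general sentence in 8.1.4 should shrink to one category with no reason recorded.

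On the hypersensitivity row, the restriction is the protocol's own, so the SAP has made no error. At 0.25 to 1 expected patient, overlap between term rows could be settled from the listing. Protocol 8.1 also asks investigators to record a syndrome rather than its separate signs where possible, which limits one patient spreading over several terms. That makes the any-grade row an improvement and not a correction.

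Four stronger readings are tempting but not supported:

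- A reader might infer that milder reactions go unreported. They remain in the event tables and listings.
- A reader might take the fever, rash and eosinophilia in Protocol 4.3, or the bronchospasm in 8.2, as the protocol scattering hypersensitivity over many terms. The first is a liver discontinuation criterion tied to raised transaminases. The second is an example of a serious event.
- A reader might infer that the causality rating behind a drug reaction is unsettled, because Protocol 9.2.4 speaks of "the relationship to study drug as assessed by the Investigator" and that Investigator is unblinded. Protocol 5.4.1 and SAP 3.3.1 have both raters assess causality in Part A and let the blinded assessor prevail on disagreement.
- A reader might fault the conjunction of severe with serious as ambiguous. The phrase is carried over from the protocol, and no consequence has been shown.

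**Conclusion.** The mismatch is real and minor. The protocol announces comparisons for hypersensitivity and emergent infections that the SAP does not plan. C. difficile infection is the SAP's own addition, so comparing it is a matter of consistency and not a protocol commitment. No event is lost, and neither the mortality analysis nor the nephrotoxicity test is touched.

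The value of the missing comparisons is uneven. For hypersensitivity at the rate reported so far, the interval would span several points either side of zero and say little. For emergent infections it would say more, at roughly ±9 to ±13 points. Both statements rest on about 100 treated patients per arm and on assumed event rates. The infection rates have no source in the documents.

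**What to change.** In SAP 9.4.1:

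1. For hypersensitivity, emergent infections and C. difficile infection, add the between-arm difference in proportions with a 95% interval by a score method (Newcombe or Miettinen-Nurminen), labelled descriptive. Leave the nephrotoxicity test as it is.
2. Add one row per arm for patients with any treatment-emergent event in the hypersensitivity queries, all grades and all causality. Keep the protocol's severe and serious drug-reaction definition as a sub-row beneath it.

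If the sponsor wants summaries only for these categories, the alternative to item 1 is to amend Protocol 8.1.4 or state in the SAP why only nephrotoxicity is compared.

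The cost is a few lines of SAP text and a few entries in an existing table, using events that are coded anyway. The downsides are some non-specific events in the broad row, which the sub-row separates out, and a hypersensitivity interval that will be wide.
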